### 8.4.3 Eye examination

Subjects with uncontrolled and potentially unstable diabetic retinopathy or maculopathy are not eligible as this indicates retinopathy that has recently progressed to a level that requires intervention or is approaching intervention, but has yet to be brought under control.

Results of an eye examination performed by an ophthalmologist, or equally qualified certified health care provider (e.g. optometrist) must be available and evaluated by the investigator before V2 to assess eligibility (see Section [8.1.11](#)). The eye examination should be performed as a fundus photography (e.g. 2-field 60 degree or better, colour or red-free) or by slit-lamp biomicroscopy examination (e.g. using a pre-corneal or corneal contact lens examination) and performed with pharmacologically dilated pupils unless using a digital fundus photography camera specified for non-dilated examination.

If the subject had such an eye examination performed within 90 days prior to screening, the investigator may base their evaluation upon the results of that examination. The examination must be repeated before V2 if the subject has experienced worsening of visual function since the last examination. If the applicable eye examination was performed before the subject signed the informed consent form, it must be documented that the reason for performing the examination was not related to this trial.

After V2 an eye examination performed according to above must be performed as per the flowchart in Section [2](#). An eye examination must be performed at the randomisation visit (V10) or within 14 days prior to V10 (the results do not need to be available for randomisation). If the eye examination is performed at V10, it must be performed prior to administration of randomised treatment. Eye examination obtained within 3 weeks prior to V26 is acceptable if the result is available at the visit. The investigator should indicate the outcome of each eye examination. Relevant findings prior to randomisation must be recorded as concomitant illness/medical history. Relevant findings occurring after randomisation should be reported as an AE, if applicable according to section [8.4](#).

### 8.4.4 Electrocardiogram (ECG)

A 12-lead ECG must be performed as per flow-chart (see Section [2](#)) and the assessment must be reviewed as described in Section [8.1.11](#).

Abnormal and clinically significant findings must be recorded as described in Section [8.4](#).

If an ECG-12 lead has been performed within 3 weeks prior to screening (V1), and the results are available at V1, the ECG does not need to be repeated at V1. If performed before the subject consents to participate in the trial it must be stated in the subject's medical records that this procedure was not performed in relation to the trial.

ECG obtained within 3 weeks prior to V10 and V26 is acceptable if the result is available at the visit.

#### 8.4.5 Body Measurements

**Height** (without shoes) will be measured at site in centimetres (cm) or inches (in) and recorded to one decimal place in the eCRF.

**Body weight** should be measured in kilograms (kg) or pounds (lb) without shoes and wearing only light clothing. Body weight must be measured prior to the start of the meal test at V10 and V26/V26A.

Body weight will be recorded to one decimal place. The body weight should be assessed on the same weighing scale throughout the trial, if possible.

**BMI** will automatically be calculated by the eCRF.

#### 8.4.6 Physical examination

Physical examination will include examination of:

- Respiratory system
- Cardiovascular system
- Central and peripheral nervous system
- Gastrointestinal system, including the mouth
- Skin

Abnormal and clinically significant findings must be recorded as described in Section [8.4](#).

#### 8.4.7 Vital signs

Diastolic blood pressure, systolic blood pressure and pulse should be measured while the subject is in a sitting position and after 5 minutes of rest.

At screening (V1) blood pressure needs to be measured three times and all values should be recorded in the eCRF. The mean value will be calculated by the eCRF, and must be used to assess the relevant exclusion criterion; please see Section [6.3](#).

### 8.5 Laboratory assessments

Except for urine pregnancy testing, which will be performed locally, all laboratory analyses will be performed by a central laboratory contracted by Novo Nordisk. The central laboratory will provide all laboratory supplies for the sampling and transportation of all blood samples taken during the trial.

Protocol  
Trial ID: NN1218-4357  
UTN: U1111-1197-8289

**CONFIDENTIAL**

Date:  
Version:  
Status:  
Page:

30 November 2020  
5.0  
Final  
57 of 105

**Novo Nordisk**

A detailed description of the procedures for obtaining the samples, handling, storage, and shipment of the samples is specified in a trial-specific laboratory manual provided to the sites by the central laboratory. Information regarding laboratory materials such as tubes and labels is also described.

Laboratory samples can be drawn on another day than on the day of the actual visit, as long as it is within the visit window, as stated in the flowchart in Section 2.

If laboratory samples need to be retaken due to missing result(s) (e.g. haemolysed, sample leaked during transit, sample not being conclusive, lost in transit, etc.), the subject should be called in for resampling. Please see the laboratory manual for further guidance.

Samples will be coded in order to keep subject's identity anonymous.

The laboratory provides results to the trial sites on an ongoing basis. The results will be transferred to the trial database.

The laboratory equipment may provide analyses not requested in the protocol but produced automatically in connection with the requested analyses according to specifications in the laboratory standard operating procedures. Such data will not be transferred to the trial database, but abnormal values will be reported to the investigator. The investigator must review all laboratory results for concomitant illnesses and AEs and report these according to Section 8.2.4 and Section 12. Review of laboratory reports must be performed as described in Section 8.1.11.

Only laboratory samples specified in the protocol must be sent to the central laboratory for analysis; if additional laboratory sampling is needed, e.g. to follow up on AEs, this must be done at a local laboratory.

Laboratory samples will be destroyed no later than the finalisation of the clinical trial report, or according to local regulations for the destruction of blood samples.

## **8.5.1      Laboratory assessments for efficacy**

### **Glucose metabolism**

PG will be measured during the meal test. See Section 8.3.1.

FPG is measured in order to evaluate metabolic control. The subject must attend these visits fasting. For definition of fasting, see Section 8.1.5

A FPG result  $\leq$  3.9 mmol/L (70 mg/dL) should not be reported as a hypoglycaemic episode but as a AE at the discretion of the investigator (see Section 12.1.1).

Blood samples will be drawn to determine the HbA1c level in order to evaluate metabolic control.

## Lipids

Blood samples for lipids will be analysed to determine:

- Triglycerides
- Total cholesterol
- High density lipoprotein (HDL) cholesterol
- Low density lipoprotein (LDL) cholesterol

## 8.5.2 Laboratory assessments for safety

### Biochemistry

Blood samples for biochemistry will be analysed to determine:

- alanine aminotransferase (ALT)
- aspartate aminotransferase (AST)
- albumin
- alkaline phosphatase
- creatinine
- creatinine clearance
- potassium
- sodium
- total bilirubin
- total protein
- eGFR at screening

eGFR will be calculated by the central laboratory based on the creatinine value using the CKD-EPI equation in order to access exclusion criteria 16.

### Haematology

Blood samples for haematology will be analysed to determine:

- haemoglobin
- haematocrit
- erythrocytes
- leucocytes
- thrombocytes

### Pregnancy testing

For females of childbearing potential (see Section 8.2.7), a blood human Chorion Gonadotropin (hCG) pregnancy test will be performed at the visits indicated in the flowchart in Section 2. In addition, urine pregnancy tests will be performed locally during the trial if pregnancy is suspected

Protocol  
Trial ID: NN1218-4357  
UTN: U1111-1197-8289

**CONFIDENTIAL**

Date:  
Version:  
Status:  
Page:

30 November 2020  
5.0  
Final  
59 of 105

**Novo Nordisk**

or if required by local law. A positive urine test should be followed by a confirmatory serum-hCG (central laboratory).

The central laboratory will provide the pregnancy kits for urine testing performed locally at the site.

## **8.6 Other assessments**

### **8.6.1 Training in the pen-injector**

The subjects must be trained in how to handle the pen-injector when handed out the first time. Training must be repeated during the trial at regular intervals in order to ensure correct use of the device.

The following should be emphasised:

- Always use a new needle for each injection as this will prevent contamination and blocked needles
- Remember to prime the pen to ensure product flow
- The needle should be kept in the skin while counting slowly to 6 after the dose counter has returned to zero after injection. If the needle is removed too early then the full dose may not have been delivered
- Always check that the correct pen is used (bolus or basal) e.g. by colour coding and label. Use the differentiation guide as a reference
- In-use time and storage conditions of pen-injectors (Section 9.3)

### **8.6.2 Diary**

At visit 1 the subjects will be provided with a diary to capture health issues (adverse events and changes in concomitant medication) only. At the run-in visit (V2) the subjects will be provided with a diary to capture health issues (adverse events and changes in concomitant medication), hypoglycaemia, SMPGs and dose data. The investigator must carefully instruct the subject in how to use the diary. All data entered in the diary is considered source data, as described in sections 8.3.2, 8.3.3 and 8.4.2. The recordings must be reviewed as described in Section 8.1.11 and transcribed, as applicable. Entries in the diaries are only to be made by the subject, unless otherwise specified.

Selected titration data (e.g. certain SMPGs and dose data) will only be used during the trial for central titration surveillance, to ensure compliance with the titration guideline (Appendix A1 and A2), and will not be reported in the clinical trial report (CTR). All data will be stored by Novo Nordisk (Section 24).

## **8.7 Subject compliance**

Throughout the trial, the investigator will remind the subjects to follow the trial procedures and requirements to ensure subject compliance.

Protocol  
Trial ID: NN1218-4357  
UTN: U1111-1197-8289

**CONFIDENTIAL**

Date:  
Version:  
Status:  
Page:

30 November 2020  
5.0  
Final  
60 of 105

**Novo Nordisk**

**Treatment compliance:** During treatment with trial products, the investigator will at each weekly contact (visit or phone contact) assess the subject's compliance by evaluating the glycaemic control, adherence to treatment and completion of the subject's diary including the SMPG profiles, dose and hypoglycaemia reporting. In addition, subject compliance will be assessed by monitoring of drug accountability at specified visits, please refer to the flow chart (Section 2).

If a subject is found to be non-compliant, the investigator will remind the subject of the importance of following the instructions given including taking the trial products as prescribed.

## 9 Trial supplies

Trial supplies comprise trial products and auxiliary supplies. Additional details regarding trial supplies can be found in the Trial Materials Manual (TMM).

Trial products must not be dispensed to any person not included in the trial.

Trial products must not be used, if they do not appear clear and colourless.

### 9.1 Trial products

The following trial products will be provided by Novo Nordisk A/S, Denmark:

**Table 9–1 Trial products (IMPs)**

Trial product	Strength	Dosage form	Route of administration	Container/delivery device
Faster aspart (test product, blinded)	100 U/mL	Solution for injection	Subcutaneously	3 mL PDS290 pen-injector
Insulin aspart (reference therapy, blinded)				
Insulin deglude (open label)	100 U/mL	Solution for injection	Subcutaneously	3 mL PDS290 pen-injector
Insulin aspart (open label for the run-in period)	100 U/mL	Solution for injection	Subcutaneously	3 mL PDS290 pen-injector

Metformin is a Non-Investigational Medicinal Product (NIMP) and will not be supplied by Novo Nordisk. However, metformin will be reimbursed if required according to local regulations.

In the treatment period the investigational medicinal products (IMPs) faster aspart and insulin aspart are visually identical.

### 9.2 Labelling

The trial products will be labelled in accordance with Annex 13, local regulations and trial requirements.

Each trial site will be supplied with sufficient trial products for the trial on an ongoing basis controlled by the IWRS. Trial products will be distributed to the trial sites according to enrolment and randomisation.

Protocol  
Trial ID: NN1218-4357  
UTN: U1111-1197-8289

CONFIDENTIAL

Date:  
Version:  
Status:  
Page:

30 November 2020  
5.0  
Final  
62 of 105

Novo Nordisk

The investigator must document that direction for use (DFU) is given to the subject orally and in writing at the first dispensing visit (V2). Additionally, the pen differentiation guide must be provided to subjects at randomisation (V10). DFU and pen differentiation guide can be provided as needed at the following dispensing visits.

### 9.3 Storage

**Table 9–2 Storage conditions**

Trial product	Storage conditions (not-in-use)	In-use conditions	In-use time a
Faster aspart	Store in refrigerator (2°C - 8°C) Do not freeze Protect from light	Store below 30°C Do not refrigerate Do not freeze Protect from light	Use within 4 weeks
Insulin aspart (NovoRapid®)	Store in refrigerator (2°C - 8°C) Do not freeze Protect from light	Store at 2°C- 30°C Do not freeze Protect from light	Use within 8 weeks
Insulin degludec	Store in refrigerator (2°C - 8°C) Do not freeze Protect from light	Store at 2°C- 30°C Do not freeze Protect from light	Use within 8 weeks

a In-use time starts when first dose is taken

The investigator must ensure that trial product is kept under proper storage conditions and record and evaluate the temperature. The investigator must inform Novo Nordisk **immediately** if any trial product has been stored outside specified conditions (e.g. outside temperature range). Additional details regarding handling of temperature deviations can be found in the TMM.

Trial product that has been stored improperly must not be dispensed to any subject before it has been evaluated and approved for further use by Novo Nordisk. The investigator must take appropriate action to ensure correct storage.

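### Does Table 9-2 leave a blinded site unable to tell how an in-use blinded bolus pen should be stored and for how long?

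*Protocol*

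**What the plan says.** Protocol Section 9.3, Table 9-2, has three rows: faster aspart, insulin aspart (NovoRapid) and insulin degludec. Unopened product has the same refrigerated storage in all three. In use, the faster aspart row reads "Store below 30°C Do not refrigerate Do not freeze Protect from light" with a limit of 4 weeks from first dose. The NovoRapid row reads "Store at 2°C- 30°C Do not freeze Protect from light" and "Use within 8 weeks", and the degludec row is the same as NovoRapid.

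Table 9-1 in Section 9.1 lists insulin aspart twice, as "Insulin aspart (reference therapy, blinded") and as "Insulin aspart (open label for the run-in period"). It adds that in the treatment period "faster aspart and insulin aspart are visually identical". Section 11 blinds investigator, subject and sponsor to the bolus treatment.

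The pen-training list in Section 8.6.1 includes "In-use time and storage conditions of pen-injectors (Section 9.3"), and training is to be repeated during the trial. Section 9.3 tells the investigator to inform the sponsor at once "if any trial product has been stored outside specified conditions (e.g. outside temperature range"). Sections 9 and 9.3 refer to the Trial Materials Manual for further detail, and Section 9.2 covers labels and the directions for use.

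**The concern.** Training after randomisation points to a table organised by product, while the person giving the training does not know which product the subject holds. For an opened blinded pen that has been in a refrigerator, or is in weeks 5 to 8 of use, the two rows give opposite answers.

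Two harms could follow. A site might ask which product it has in order to settle a storage question, or row-specific instructions might reach subjects and reveal the arm. Alternatively, subjects who learned the looser rule during eight weeks on open-label NovoRapid and degludec might carry it over after V10. Only faster aspart pens would then fall outside their stated limits, so the handling error would be one-sided.

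**Working it through.** The plan states no figure on this point, so the check is a comparison of text with some arithmetic on how far the time limit matters.

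**1. The rows side by side (Table 9-2)**

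| | Faster aspart | NovoRapid | Can one pen meet both? |
|---|---|---|---|
| Unopened | Refrigerator, 2-8°C | Refrigerator, 2-8°C | Yes, identical |
| In use, temperature | Below 30°C, not refrigerated | 2-30°C | Yes, where the two ranges overlap |
| In use, time | 4 weeks = 28 days | 8 weeks = 56 days | Yes, up to 28 days |

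The faster aspart limits lie essentially inside the NovoRapid limits. No circumstance arises in which meeting one row breaks the other.

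**2. What a blinded site has to decide**

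A blinded bolus pen is one of two known products. If it is inside both rows, nothing needs doing. If it is outside either row, the site can inform the sponsor. Section 9.3 does not ask the site to identify the row first, so the same action is open to it in both arms. The text on recording temperature and withholding product from dispensing reads most naturally as site stock, where all rows agree. Its extension to a pen at a subject's home is an inference.

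**3. Tables 9-1 and 9-2**

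Table 9-1 counts supplies, so blinded and open-label insulin aspart are separate entries. Table 9-2 gives one storage specification per product. Section 12.4.1 likewise lists NovoRapid once for both open-label and blinded pens. The tables do not contradict each other.

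**4. When the time difference can matter**

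- Pen content: 3 mL × 100 U/mL = 300 U (Table 9-1).
- A pen outlasts 28 days only below 300/28 = 10.7 U/day of bolus insulin, with one pen in use and no priming. At 10 U/day it lasts 300/10 = 30 days; at 11 U/day, 300/11 = 27.3 days.
- Section 8.6.1 requires priming, and Section 5.3 specifies three main-meal injections a day. The priming volume is not given. Assuming 1 to 2 U each time, the limit falls to 10.7 − 3 = 7.7 U/day or 10.7 − 6 = 4.7 U/day.

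Appendix A1, Table 2 shows total bolus start doses from 4 to 48 U/day in 36 rows. Rows below each limit:

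| Priming (assumed) | Limit, U/day | Ratio 40:60 | Ratio 60:40 |
|---|---|---|---|
| None | 10.7 | 4 of 36 | 9 of 36 |
| 1 U | 7.7 | 2 of 36 | 5 of 36 |
| 2 U | 4.7 | 0 of 36 | 1 of 36 |

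These are rows of a lookup table, not subjects. Table 2 serves T1DM subjects transferring from premix; those already on bolus insulin transfer unit for unit (Appendix A1, Table 3). The doses apply at V2, eight weeks before any blinded pen is used, and bolus insulin is titrated weekly after V10. The counts therefore cannot be turned into a number of subjects affected. Dispensing intervals would also limit the time difference, but the visit grid is not readable in the text available. The refrigeration difference does not depend on dose.

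**5. Link to the analysis**

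The estimand, sample size and primary model in protocol Section 17 and the SAP use nothing from Table 9-2. If some faster aspart pens were mishandled and lost effect (an assumption; the documents give no potency data), HbA1c in that arm would tend to rise. That moves the difference, faster aspart minus NovoRapid, towards the 0.4% margin and so against the non-inferiority claim. Weekly titration would offset part of it. The hypoglycaemia comparison could move the other way, by an amount that cannot be computed.

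**The case for a change.** The strongest case is that a workable rule left unwritten will not be applied uniformly. Section 8.6.1 cites Section 9.3 as the source for in-use time and storage, so Table 9-2 is where a trainer looks. The directions for use must be given at V2, but at V10 only the pen differentiation guide is mandatory, and nothing in the protocol prompts a change of storage habit when some subjects move to a product with tighter limits. Neither reference to the Trial Materials Manual says that it contains a rule for blinded pens.

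The factual part stands: the protocol does not state which in-use instruction governs a blinded pen. The harm does not follow from it. No passage shows instructions that differ by arm reaching a site or subject. Carry-over from the run-in is speculation, since training is repeated with storage as one of its topics and the directions for use can be reissued at later dispensing visits. The unseen documents show neither that a common instruction exists nor that it is absent.

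**Conclusion.** No change to the plan is called for. The protocol omits a single in-use instruction for the blinded bolus pens, but the two product rows are compatible, so a site can comply with both and report any departure from either while staying blinded. Detail of this kind belongs naturally on the label, in the directions for use and in the Trial Materials Manual.

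The rows differ on two in-use attributes. The time difference is confined to total bolus use below about 10.7 U/day, or 4.7 to 7.7 U/day under the priming assumption, with one pen in use at a time. The number of subjects affected cannot be derived from the documents. No unblinding or bias is demonstrated, and neither the primary analysis nor its conclusion depends on the point. The conclusion would be different if labels or site instructions were found to give arm-specific storage rules for the blinded pens; nothing in the protocol or SAP suggests that they do.

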### 9.4 Drug accountability and destruction

Drug accountability of all trial products received at site is the responsibility of the investigator.

Each trial product package is referred to as a dispensing unit (DU) and is uniquely numbered with a Dispensing Unit Number (DUN).

Returned trial product (used/partly used and/or unused), expired or damaged trial product can be stored at room temperature and must be stored separately from non-allocated trial product.

Investigator should instruct the subjects in what to be returned at the next visit.

Protocol  
Trial ID: NN1218-4357  
UTN: U1111-1197-8289

CONFIDENTIAL

Date:  
Version:  
Status:  
Page:

30 November 2020  
5.0  
Final  
63 of 105

Novo Nordisk

Non-allocated trial products (expired, damaged or available) must be accounted as unused at the latest at closure of the trial site.

Destruction of trial products can be performed on an ongoing basis and will be done according to local procedures after accountability is finalised and reconciled by the monitor. Destruction of products must be documented in the IWRS.

## 9.5 Auxiliary supplies

The following will be provided by Novo Nordisk in accordance with the TMM:

- DFU for the prefilled pens
- Novo Nordisk needles for the pen devices
- BG meters and auxiliaries for the BG meters
- Standardised liquid meal (for the meal test)

Only needles provided by Novo Nordisk with a maximum length of 6 mm must be used for administration of trial product.

